13.0 Overall Type-I Error Control

Due to the Phase 2 nature of the phase 2 study, all the endpoints will be tested at a two-sided significance level of 0.1 and overall type-1 error control is not considered necessary.

14.0 Version History

Table 4. SAP Version History Summary

Version	Date	Summary
1.0	30 July 2021	Original version
2.0	27 December 2022	
• Modify the ITT and Safety Population to ITT_1/ITT_2, Safety_1/Safety_2 Population.• Removed Baseline PhGIC-V and T-PaGVA from the disease characteristic table in Section 7.1• Added NRI-MI approach for subject who have opportunity to reach Week 52 for F-VASI 50, F-VASI 75, T-VASI 50. In addition, percent change from Baseline in F-VASI, T-VSI and change from Baseline in VitiQoL question 16 are added in Section 9.5• Added additional efficacy subgroup analyses in Section 9.6• Update severity to toxicity in Treatment Emergent Adverse Events by SOC and/or PT in Section 10.2.3• Added a post-Baseline treatment ECT listing in Section 10.6• Clarify the efficacy and safety analyses for each analysis population

Appendix A. Protocol Deviations

The number and percentage of subjects who reported at least one of the following protocol deviation categories will be provided.

- Subject entered into the study even though s/he did not satisfy entry criteria.
- Subject developed withdrawal criteria during the study and was not withdrawn.
- Subject received wrong treatment or incorrect dose of study.
- Subject took prohibited concomitant medication.

Appendix B. Definition of Adverse Events of Special Interest

Adverse Events of Special Interest (AESI) will be identified using the following search criteria:

AESI	Type of MedDRA Query	Broad or Narrow Search	SMQ/CMQ Search Criteria
Serious Infections	CMQ		"Infections" – Subset for SAEs
Opportunistic Infection excluding tuberculosis and herpes zoster	CMQ		"Opportunistic Infection excluding tuberculosis and herpes zoster"
Possible malignancy	SMQ	Narrow	"Malignancies"
Malignancy	SMQ		"Malignant Tumours"
Non-Melanoma Skin Cancer (NMSC)	SMQ/CMQ	SMQ Narrow	Skin Malignant tumours (Narrow SMQ) removing Melanoma CMQ
Malignancy excluding NMSC			Malignancy Narrow SMQ and removing NMSC output
Lymphoma	SMQ		"Malignant Lymphomas"
Hepatic Disorder	SMQ	Narrow	"Drug Related Hepatic Disorders"
Adjudicated Gastrointestinal Perforations	Medical review of events identified by the "Gastrointestinal Perforation" SMQ	Narrow search	
Anemia	CMQ		"Non-Hemolytic and Non-Aplastic Anemias"
Neutropenia	CMQ		"Hematological Toxicity – Neutropenia"
Lymphopenia	CMQ		"Hematological Toxicity – Lymphopenia (Veliparib Product Specific)"
Herpes Zoster	CMQ		"Herpes Zoster"
Renal Dysfunction	SMQ	Narrow	"Acute Renal Failure"

AESI	Type of MedDRA Query	Broad or Narrow Search	SMQ/CMQ Search Criteria
Active Tuberculosis	CMQ		"Active Tuberculosis"
Adjudicated cardiovascular events ^a	Output from CAC		
MACE*			
Cardiovascular Death			
Non-fatal Myocardial Infarction			
Non-fatal Stroke			
Other Adjudicated Cardiovascular Events			
Undetermined/Unknown Cause of Deaths			
Adjudicated Thrombotic Events	Output from CAC		
VTE**			
Deep Vein Thrombosis			
Pulmonary Embolism			
Other Venous Thrombosis			
Arterial Thromboembolic Events (non-cardiac, non-neurologic)			

CAC = Cardiovascular Adjudication Committee; CMQ = company MedDRA query; PT = preferred term; SMQ = standard MedDRA query

* MACE: Major Adverse Cardiovascular Events, defined as cardiovascular death, non-fatal myocardial infarction and non-fatal stroke.

** VTE: Venous thromboembolic events, defined as deep vein thrombosis (DVT) and pulmonary embolism (PE) (fatal and non-fatal).

a. Reviewed and adjudicated by an independent Cardiovascular Adjudication Committee in a blinded manner.

Appendix C. Potentially Clinically Important Criteria for Safety Endpoints

The criteria for Potentially Clinically Important (PCI) laboratory findings are described in Table C-1 and Table C-2, and the PCI criteria for vital sign findings are described in Table C-3.

Table C-1. Criteria for Potentially Clinically Important Hematology Values

Hematology Variables	Units	Definition of Potentially Clinically Important (NCI CTCAE Grade 3 or higher)
		Very Low
Hemoglobin	g/dL	< 8.0
Platelets count	10 ⁹ /L	< 50.0
WBC count	10 ⁹ /L	< 2.0
Neutrophils	10 ⁹ /L	< 1.0
Lymphocytes	10 ⁹ /L	< 0.5

Note: A post-baseline value must be more extreme than the Baseline value with at least one CTCAE grade of worsening to be considered a potentially clinically important finding.

Table C-2. Criteria for Potentially Clinically Important Chemistry Values

Chemistry Variables	Units	Definition of Potentially Clinically Important (NCI CTCAE Grade 3 or higher)	
		Very Low	Very High
ALP	U/L		$> 5.0 \times \text{ULN}$
SGOT/AST	U/L		$> 5.0 \times \text{ULN}$
SGPT/ALT	U/L		$> 5.0 \times \text{ULN}$
Albumin	g/L	< 20	
Glucose	mmol/L	< 2.2	> 13.9
Triglycerides	mmol/L		> 5.7
Creatinine	mcmol/L		$> 3.0 \times \text{ULN}$
Potassium	mmol/L	< 3.0	> 6.0
Calcium	mmol/L	< 1.75	> 3.1
Sodium	mmol/L	< 130	> 155
Phosphate	mmol/L	< 0.6	
Total Cholesterol	mmol/L		> 10.34

Note: A post-baseline value must be more extreme than the Baseline value with at least one CTCAE grade of worsening to be considered a potentially clinically important finding.

Table C-3. Criteria for Potentially Clinically Important Liver Function Tests

Variables	Units	Definition of Potentially Clinically Important
		Very High
AST	U/L	$\geq 3 \times \text{ULN}$
		$\geq 5 \times \text{ULN}$
		$\geq 10 \times \text{ULN}$
		$\geq 20 \times \text{ULN}$
ALT	U/L	$\geq 3 \times \text{ULN}$
		$\geq 5 \times \text{ULN}$
		$\geq 10 \times \text{ULN}$
		$\geq 20 \times \text{ULN}$
Total Bilirubin	UMOL/L	$\geq 2 \times \text{ULN}$
Alkaline phosphatase	U/L	$\geq 1.5 \times \text{ULN}$
ALT (U/L) and/or AST (U/L) and concurrent TBL (UMOL/L)		ALT and/or AST $\geq 3 \times \text{ULN}$ and concurrent TBL $\geq 1.5 \times \text{ULN}$ ALT and/or AST $\geq 3 \times \text{ULN}$ and concurrent TBL $\geq 2 \times \text{ULN}$

Table C-4. Criteria for Potentially Clinically Important Vital Sign Values

Vital Sign	Category	Criteria for Potential Clinically Significant Vital Signs
Systolic blood pressure	Low	Value ≤ 90 mmHg and decrease ≥ 20 mmHg from Baseline
	High	Value ≥ 160 mmHg and increase ≥ 20 mmHg from Baseline
Diastolic blood pressure	Low	Value ≤ 50 mmHg and decrease ≥ 10 mmHg from Baseline
	High	Value ≥ 100 mmHg and increase ≥ 10 mmHg from Baseline
Pulse	Low	Value ≤ 50 bpm and decrease ≥ 15 bpm from Baseline
	High	Value ≥ 120 bpm and increase ≥ 15 bpm from Baseline
Weight	High	$> 7\%$ increase from Baseline
	Low	$> 7\%$ decrease from Baseline

Appendix D. Random Seeds

In case of non-convergence, the random seed will be updated by adding 10000 at each attempt until convergence of model happens.

A. Random Seeds for NRI-MI

Endpoints	Random Seed	
	MCMC procedure	PROC MI
F-VASI 50	1001	9001
F-VASI 75	1002	9002
F-VASI 90	1003	9003
T-VASI 50	1004	9004
T-VASI 75	1005	9005
T-VASI 90	1006	9006
VNS 4/5	1007	9007
DLQI 0/1	1008	9008
PhGIC-V 1/2	1009	9009
PaGIC-V 1/2	1010	9010
F-PhGVA 0/1	1011	9011
T-PhGVA 0/1	1012	9012
F-PaGVA 0/1	1013	9013
T-PaGVA 0/1	1014	9014
DLQI 4	1015	9015

B. Random Seeds for MI

Endpoints	Random Seed	
	MCMC procedure	PROC MI
Percent change from Baseline in F-VASI	1015	9015

Appendix E. Non-Responder Imputation Incorporating Multiple Imputation to Handle Missing Data Due to COVID-19 Pandemic or Any Other Missing Data that Can Be Reasonably Assumed to Be Missing at Random for Dichotomized Outcome Variables

1.0 Overview

1.1 Background and Justification for Missing at Random (MAR) Assumption

The COVID-19 pandemic is interfering with the conduct of many ongoing trials, with potential impacts on treatment duration and the collection, analysis and the interpretation of clinical trial data. Some protocol-specified visits in the clinical trials may be impacted due to COVID-19 infection or logistical restrictions during the pandemic. For example, some scheduled visits may be missed due to self-quarantine or local government restrictions on travel; some visits may also be delayed or canceled due to healthcare resource constraints during the pandemic. Impacted visits due to COVID-19 will be recorded in the database. The probability of having missed visits and missing data due to COVID-19 infection or logistical restrictions related to the COVID-19 pandemic can be reasonably assumed to be unrelated to the unobserved values. Therefore, for the purpose of statistical analysis, it is reasonable to assume that these missing data are missing at random (MAR) and the statistical models that require MAR assumption are appropriate. In some cases, sensitivity analyses may be performed to assess the impact of missing data and the robustness of the conclusion.

1.2 FDA Guidance

FDA provided two guidance documents^{1,2} in March 2020 and June 2020 on the efficacy collection and possible changes in the statistical analysis plan:

- "With respect to efficacy assessments, FDA recommends consultation with the appropriate review division regarding protocol modifications for the collection of efficacy endpoints, such as use of virtual assessments, delays in assessments, and alternative collection of research-specific specimens, if feasible. For individual instances where efficacy endpoints are not collected,

the reasons for failing to obtain the efficacy assessment should be documented (e.g., identifying the specific limitation imposed by COVID-19 leading to the inability to perform the protocol-specified assessment)."

- "If changes in the protocol will lead to amending data management and/or statistical analysis plans, the sponsor should consider doing so in consultation with the applicable FDA review division. Prior to locking the database, sponsors should address in the statistical analysis plan how protocol deviations related to COVID-19 will be handled for the prespecified analyses."

1.3 EMA Guidance

EMA provided guidance³ in March 2020:

- "At this point in time it is not possible to give general applicable advice on how the different aspects related to the pandemic should be handled, as implications on clinical trials are expected to be manifold. Impact on the data collection, analysis and interpretation of results for each trial will need a thorough case-by-case assessment."
- "As a general principle, there are strong scientific reasons to conduct trials as planned and implement changes only when there is a convincing scientific reason that it improves interpretability of results."

1.4 Missing Data Handling for Missing Due to COVID-19 for Dichotomized Variables

In this document, a missing data handling method is proposed to handle missing data due to COVID-19 infection or logistical restrictions related to the COVID-19 pandemic under the general MAR framework. In particular, we explain using multiple imputation (MI) to handle missing data due to COVID-19 or any other missing data that can be reasonably assumed to be Missing at Random in dichotomized variables in conjunction with non-responder imputation (NRI) for missing data due to other reasons.

2.0 Non-responder Imputation Incorporating Multiple Imputation (NRI-MI)

2.1 Overall Description of the Method

For a dichotomized outcome variable with missing data, the NRI-MI will categorize any subject who does not have evaluation during a pre-specified visit window as a non-responder for the visit, with two exceptions:

- If the subject is a responder both before and after the pre-specified visit window in Period 1, the subject will be categorized as a responder for the visit.
- If the reason for missing (e.g., missed visits, incomplete visit, out-of-schedule visits, or discontinuations of study drug) is due to COVID-19 or any other missing data that can be reasonably assumed to be Missing at Random, the information will be captured in the database and the subject's response status will be imputed using multiple imputation.

In addition, subjects whose change/percent change from Baseline cannot be calculated because of a missing Baseline will be considered as a non-responder at all post-baseline visits unless the post-baseline value is zero.

Non-responder imputation incorporating multiple imputation (NRI-MI) for missing due to COVID-19 or any other missing data that can be reasonably assumed to be Missing at Random will be implemented as follows.

2.2 Multiple Imputation (MI) and MAR Assumption

When a dichotomized variable is derived from a continuous scale, for example, F-VASI 75 (at least a 75% reduction in F-VASI relative to Baseline), the multiple imputation will be applied to the original scale, F-VASI (ranges from 0 – 100) assuming multivariate normal distribution. Then the dichotomized variable will be derived from the imputed value.

The MI procedure assumes that the data are missing at random (MAR). That is, for an outcome variable Y, the probability that an observation is missing depends only on the observed values of other variables, not on the unobserved values of the outcome variable Y. Statistical inference from the MI procedure is valid under the MAR assumption.

2.3 Imputation Algorithm

It is reasonable to assume the missing values of the longitudinal data for an outcome variable (e.g., F-VASI, the original scale of F-VASI 75, at each post-baseline visit) follows a monotone missing pattern. In practice, the missing data of the outcome variable might have an arbitrary (non-monotone) missing data pattern. An extra step may be added accordingly, to augment data into a monotone missing pattern.

For the outcome variable (e.g., F-VASI at each visit), K 'complete' datasets can be generated in two steps: augmentation step and imputation step. K, the number of repetitions, is determined below.

Augmentation Step

For datasets with non-monotone missing data pattern, the augmentation step will first impute enough values to augment the data into a monotonic missing pattern:

Markov Chain Monte Carlo (MCMC) will be applied to augment the data using PROC MI with the MCMC IMPUTE=monotone statement, assuming a multivariate normal distribution. The augmented data will be used in the subsequent imputation step to generate 'complete' datasets. Covariates included in the model are treatment, stratification factors (the age group [≤ 50 and > 50], Baseline disease severity [T-VASI < 15 and ≥ 15], and status of active vitiligo [Yes/No]), Baseline, and all post-baseline visits of the outcome variable according to the pre-specified order. For T-VASI related endpoints, Baseline disease severity (T-VASI < 15 and ≥ 15) will not be included in the model. Of note, categorical variables are included using the form of dummy variables.

Repeat the imputation process K=30 times using the procedure described above to form K=30 monotone missing datasets, where K is determined as described in "Repetition of Imputations (K)."

Imputation Step

For missing data with monotone missing patterns, the choice of multiple imputation using a parametric regression model that assumes multivariate normality is appropriate.

The imputation step is described below:

- The imputation model for the missing data is a regression model, which controls for treatment, stratification factors (the age group [≤ 50 and > 50], Baseline disease severity [T-VASI < 15 and ≥ 15], and status of active vitiligo [Yes/No]), Baseline, and all post-baseline visits of the outcome variable. For T-VASI related endpoints, Baseline disease severity (T-VASI < 15 and ≥ 15) will not be included in the model. The covariates included in the model and the order of these variables are consistent with the augmentation step.
- For each monotone missing dataset, using SAS PROC MI with MONOTONE REG model statement, the outcome variable at each post-baseline visit with missing values will be imputed sequentially with covariates constructed from their corresponding sets of preceding variables.

A 'complete' dataset with imputed values for the missing data is generated after the augmentation and imputation steps are completed.

Repetition of Imputations (K)

Repetition of imputations, K, must be determined in advance. When estimating the overall variance of multiple imputation, the additional sampling variance is the between-imputation variance divided by K. This value represents the sampling error associated with the overall or average coefficient estimates. It is used as a correction factor for using a specific number of imputations. The more imputations (K) are conducted, the more precise the parameter estimates will be. For example, with a 1% power falloff tolerance

in multiple imputation, as compared to an infinite number of imputations, multiple imputation requires 20 repetitions of imputation for 30% missing information and 40 repetitions for 50% missing information.⁴ In the usual clinical settings expecting less than 30% missing information, $K = 30$ repetitions are deemed sufficient. When missingness exceeds 30%, depending on the power falloff tolerance level, number of repetitions may need to be increased. Recent research⁴ suggested that the number of repetitions (K) should be at least equal to the percentage of missing.⁶

2.4 Derivation of Response Status and Non-Responder Imputation

For each 'complete' dataset, the imputed post-baseline values will be rounded to the same precision as the observed data. Response status (e.g., F-VASI 75 at each visit) will be determined accordingly.

The imputed response status for missing due to reasons other than COVID-19 or any other missing data that can be reasonably assumed to be Missing at Random will be overridden by non-responder imputation (Section 2.1) to ensure that multiple imputation is only applied to missing due to COVID-19 or any other missing data that can be reasonably assumed to be Missing at Random:

- Using NRI approach, all missing due to reasons other than COVID-19 or any other missing data that can be reasonably assumed to be Missing at Random will be categorized as non-responders. In addition, subjects whose change/percent change from Baseline cannot be calculated because of a missing Baseline will be considered as a non-responder at all post-baseline visits unless the post-baseline value is zero.
- The only exception is that a subject will be categorized as a responder for the visit if the subject is a responder both before and after an SAP-specified visit window in Period 1.

2.5 Analysis

The statistical analysis will use the Cochran-Mantel-Haenszel (CMH) test adjusted by the stratification factors derived from actual values.

2.5.1 Analysis of Each Dataset

For each of the K 'complete' datasets, the CMH test will be used to estimate the treatment difference versus placebo and the corresponding standard error.

2.5.2 Synthesis of Results for Statistical Inference

The results from the K 'complete' datasets will be synthesized using the SAS procedure PROC MIANALYZE, following Rubin's formula (Rubin, 1987⁵), to derive the MI estimator of the treatment difference for the final inferences.

Rubin's formula

We fit the analysis model to the k^{th} 'complete' dataset, denoting the estimate of the treatment difference q by $\tilde{\theta}_k$ from the k^{th} 'complete' dataset, and denoting the corresponding estimate of the variance as V_k .

The MI estimator of q (point estimator obtained from PROC MIANALYZE), $\tilde{\theta}_{MI}$, is the average of the K individual estimators:

$$\tilde{\theta}_{MI} = \frac{1}{K} \sum_{k=1}^K \tilde{\theta}_k.$$

The estimated variance of $\tilde{\theta}_{MI}$, is a combination of the between- and within-imputation variability as follows:

$$V_{MI} = W + (1 + \frac{1}{K})B,$$

where $W = \frac{1}{K} \sum_{k=1}^K V_k$ is the within-imputation variability and $B = \frac{1}{K-1} \sum_{k=1}^K (\tilde{\theta}_k - \tilde{\theta}_{MI})^2$ is the between-imputation variance.

It has been shown¹ that the statistic

$$T = \frac{\tilde{\theta}_{MI} - \theta}{\sqrt{V_{MI}}}$$

has an approximate t_v distribution where $v = (K - 1)(1 + \frac{w}{B})^2$. Statistical inference, including hypothesis testing and confidence intervals for the treatment effect, will be based on this T-statistic.

3.0 Sample SAS Code

```
*****
/*IMPUTATION ALGORITHM*/
*****
/*NOTE: THIS APPROACH REQUIRES NO MISSING IN CATEGORICAL COVARIATES AND
REQUIRES AT LEAST ONE OBSERVATION IN BASELIBE OR ONE OF THE POST-
BASELINE VISIT*/
*****
/*PRE-AUGMENTATION - CREATE DUMMY FOR CATEGORICAL VARIABLES*/
*****
DATA VASI_2; SET VASI;
  /*THE MCMC STATEMENT BELOW ASSUMES MULTI-VARIATE NORMAL*/
  /*IF TREATMENT OR ANY COVARIATES ARE CATEGORICAL WITH L>2 LEVELS*/
  /*NEED TO CREATE L-1 DUMMY VARIABLES*/
  /*HERE, TREATMENT (TRT01PN) HAS 4 LEVELS, SO WE NEED 3 DUMMY
VARIABLES*/
  IF TRT01PN=1 THEN TRT1=1;
  ELSE TRT1=0;
  IF TRT01PN=2 THEN TRT2=1;
  ELSE TRT2=0;
  IF TRT01PN=3 THEN TRT3=1;
  ELSE TRT3=0;
RUN;
*****
/*AUGMENTATION STEP -- TO HAVE 30 MONOTONE MISSING DATASETS*/
PROC MI DATA=VASI_2 OUT=VASI_MONO NIMPUTE=30 SEED= 1001 /*RANDOM SEED
PRE-DEFINED*/
  ROUND=. . . . . 0.1 0.1 0.1 0.1 0.1 0.1 0.1 /*VALUE ROUND TO 1ST
DECIMAL*/
  MIN=. . . . . 0 0 0 0 0 0 0 /*MINIMUM VALUE OF F-VASI IS
0*/
  MAX=. . . . . 100 100 100 100 100 100 100; /*MAXIMUM VALUE OF F-
VASI IS 100*/
  MCMC IMPUTE=MONOTONE ;
```

```
/*NOTE: CATEGORICAL VARIABLES SUCH AS TRT1 TRT2 TRT3 ARE DUMMY, CREATED
ABOVE*/
/*NOTE: ALL OTHER NON-DUMMIED COVARIATES MUST BE CONTINUOUS*/
/*SUPPOSE STRATAN (NUMERIC VARIABLE FOR STRATA) HAS ONLY 2 LEVELS, NO
NEED TO CREATE DUMMY*/
  VAR TRT1 TRT2 TRT3 AGEGR1N TVAGR1N ACTVGR1N BASE WK2 WK4 WK8 WK12 WK18
WK24;
/*CAUTION TO USE THE "BY" STATEMENT IN MCMC: */
/*MVN MODEL IS FITTED WITHIN EACH 'BY' GROUP, INSTEAD OF ACROSS ALL
GROUPS*/
RUN;

/*IMPUTATION STEP – DETERMINE IMPUTATION DISTRIBUTION AND RANDOMLY
IMPUTE MISSING VALUE TO GENERATE 'COMPLETE' DATASETS*/
/*****************/
PROC MI DATA=VASI_MONO OUT=VASI_FULL NIMPUTE=1 SEED= 9001 /*RANDOM SEED
PRE-DEFINED/
  ROUND=. . . . . 0.1 0.1 0.1 0.1 0.1 0.1 0.1 /*VALUE ROUND TO 1ST
DECIMAL*/
  MIN=. . . . . 0 0 0 0 0 0 0 /*MINIMUM VALUE OF F-VASI IS
0*/
  MAX=. . . . . 100 100 100 100 100 100 100; /*MAXIMUM VALUE OF F-
VASI IS 100*/
  MINMAXITER=1000;
  CLASS TRT01PN AGEGR1N TVAGR1N ACTVGR1N;
  VAR TRT01PN AGEGR1N TVAGR1N ACTVGR1N BASE WK2 WK4 WK8 WK12 WK18 WK24;
  MONOTONE REG (WK2 WK4 WK8 WK12 WK18 WK24); /* IMPUTED SEQUENTIALLY,
FROM WK 2 TO 24, WITH COVARIATES CONSTRUCTED FROM THE CORRESPONDING
PRECEDING VARIABLES*/
  BY _IMPUTATION_; /*FOR EACH OF THE 30 MONOTONE
MISSING DATASETS, IMPUTE A 'COMPLETE' DATASET*/
RUN;

/*DETERMINE DICHOTOMOUS RESPONSE STATUS, VASI 50*/
DATA ALL; SET VASI_FULL;
  IF 0<=WK2<=0.5*BASE THEN VASI50_2=1;
  ELSE VASI50_2=0;
  IF 0<=WK4<=0.5*BASE THEN VASI50_4=1;
  ELSE VASI50_4=0;
  IF 0<=WK8<=0.5*BASE THEN VASI50_8=1;
  ELSE VASI50_8=0;
  IF 0<=WK12<=0.5*BASE THEN VASI50_12=1;
  ELSE VASI50_12=0;
  IF 0<=WK18<=0.5*BASE THEN VASI50_18=1;
  ELSE VASI50_18=0;
  IF 0<=WK24<=0.5*BASE THEN VASI50_24=1;
  ELSE VASI50_24=0;
RUN;
```

```
*****
*/
/*      DATA HANDLING STEPS TO MERGE COVID-19 or Other MAR STATUS OMITTED
*/
/*      PLACE TO ADD DATA HANDLING AND MERGING STEPS
*/
*****
*/
/*FOR MI, SKIP THE FOLLOWING CODE, PROCEED TO THE CODE AFTER ANALYSIS
MODEL *//*OVERRIDE MISSING VALUES NOT DUE TO COVID-19 or Other MAR WITH
TRADITIONAL NRI*/
DATA ALLF; SET ALL;
  /*COVID19 XX='Y' IF MISSING AT WEEK XX IS DUE TO COVID-19 or Other
MAR; IF NOT, OVERRIDE WITH TRADITIONAL NRI*/
  IF COVID19_2 NE 'Y' THEN VASI50_2=VASI50NRI_2;
  IF COVID19_4 NE 'Y' THEN VASI50_4=VASI50NRI_4;
  IF COVID19_8 NE 'Y' THEN VASI50_8=VASI50NRI_8;
  /*VARIABLE VASI50NRI_XX: TRADITIONAL NRI DATA AT WEEK XX, WHICH COVERS
THE SPECIAL HANDLING SUCH AS THE BEFORE-AND-AFTER EXCEPTION*/
  IF COVID19_12 NE 'Y' THEN VASI50_12=VASI50NRI_12;
  IF COVID19_18 NE 'Y' THEN VASI50_18=VASI50NRI_18;
  IF COVID19_24 NE 'Y' THEN VASI50_24=VASI50NRI_24;
RUN;
PROC SORT DATA=ALLF; BY _IMPUTATION_ SUBJID; RUN;

*****
/*ANALYSIS MODEL*/
*****

/*KEY CODE: ANALYZING EACH 'COMPLETE' DATASET*/
/*****
/*COMPARE TREATMENT GROUPS 1 (PLACEBO) AND 2 (HIGH-DOSE) ONLY*/
DATA ALL; SET ALL;
  WHERE TRT01PN IN (1,2);
RUN;

/*INDIVIDUAL-LEVEL DATA --> # OF RESPONDERS & # OF SUBJECTS, TO BE READ-
IN TO PROC STD RATE*/
PROC FREQ DATA=ALL;
  BY _IMPUTATION_;
  TABLES TRT01PN*AGEGR1N*TVAGR1N*ACTVGR1N*VASI50_24/LIST NOCUM NOPRINT
  OUT=COUNT_TABLE;
  /*WEEK 24 RESULTS AS AN EXAMPLE*/
RUN;
DATA COUNT_TABLE; SET COUNT_TABLE;
  DROP PERCENT;
```

```
RUN;
PROC TRANSPOSE DATA=COUNT_TABLE OUT=FREQ_TABLE PREFIX=RESP;
ID VASI50_24;
BY IMPUTATION_ TRT01PN AGEGR1N TVAGR1N ACTVGR1N;
VAR COUNT;
RUN;
DATA FREQ TABLE1; SET FREQ_TABLE;
CASE=RESP1;
SIZE=SUM(RESPO, RESP1);
KEEP _IMPUTATION_ TRT01PN AGEGR1N TVAGR1N ACTVGR1N CASE SIZE;
RUN;

/*RE-ORDER TO SET 1 (PLACEBO) AS THE REFERENCE GROUP*/
DATA FREQ_TABLE2; SET FREQ_TABLE1;
IF TRT01PN=2 THEN TRT01PN=0;
RUN;

/*CALCULATE THE COMMON RISK DIFF FOR EACH COMPLETE DATASET*/
PROC STDRATE DATA=FREQ_TABLE2
METHOD=MH STAT=RISK EFFECT=DIFF;
BY _IMPUTATION_;
POPULATION GROUP=TRT01PN EVENT=CASE TOTAL=SIZE;
STRATA AGEGR1N TVAGR1N ACTVGR1N / ORDER=DATA STATS(CL=NONE) EFFECT;
ODS OUTPUT EFFECT=EFFECT;
RUN;

/*COMBINING RESULTS USING PROC MIANALYZE*/
*****
PROC MIANALYZE DATA=EFFECT;
ODS OUTPUT PARAMETERESTIMATES=RISK_DIFF_MH;
MODELEFFECTS RISKDIFF;
STDERR STDERR;
RUN;
```

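### The sample SAS code in SAP Appendix E discards the non-responder override, so responder analyses built from it would use plain multiple imputation

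*SAP*

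**What the plan says.** The governing prose is consistent. SAP Section 9.2 makes NRI-MI the primary approach for categorical endpoints in Period 1. A subject without an evaluation in the visit window counts as a non-responder, with two exceptions: the subject responded both before and after that window within Period 1, or the value is missing because of COVID-19 or can reasonably be taken as missing at random (MAR). Only the second exception goes to MI. Appendix E Section 2.1 repeats the rule, and Section 2.4 requires the imputed status of all other missing values to be overridden as non-response. Section 9.1 sends the analysis to Appendix E when the 30 imputed datasets differ. Plain MI is planned in Section 9.2 only as a sensitivity analysis of the continuous primary endpoint.

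Appendix E ends with "3.0 Sample SAS Code". After deriving responder status from the fully imputed scores in dataset ALL, a comment says "FOR MI, SKIP THE FOLLOWING CODE, PROCEED TO THE CODE AFTER ANALYSIS". The override step follows and begins "DATA ALLF; SET ALL". Its comment notes that the NRI variable covers "THE SPECIAL HANDLING SUCH AS THE BEFORE-AND-AFTER EXCEPTION". Then comes "PROC SORT DATA=ALLF; BY _IMPUTATION_ SUBJID; RUN". The analysis block starts with "DATA ALL; SET ALL" and proceeds to "PROC FREQ DATA=ALL".

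**The concern.** The override and the before-and-after exception exist only in ALLF, and no later statement reads ALLF. The estimates are built from ALL, where every missing value has an MI-derived status whatever the reason it is missing. Both paths, plain MI and NRI-MI, therefore end in the plain-MI analysis.

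At stake are the responder endpoints: F-VASI 75, F-VASI 50 and T-VASI 50 at Week 24 among the secondary endpoints, and the additional responder endpoints listed in SAP Section 3.3. This is the only code in the appendix to which Section 9.1 refers. It carries this study's visits and strata and the Appendix D seeds for F-VASI 50 (1001 and 9001), so a programmer could plausibly start from it. The mistake would be silent, because the code as traced would still give plausible estimates.

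**Working it through.** **Dataset trace (SAP Appendix E, Section 3.0)**

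1. ALL is created from the fully imputed dataset. Response is set from the imputed F-VASI for every missing value.
2. ALLF is created from ALL. Where the missing value is not flagged as COVID-19 or other MAR, response is replaced by the NRI status. A step that writes ALLF leaves ALL unchanged.
3. ALLF is sorted. This is its last mention.
4. ALL is subset to two treatment groups and written back to ALL.
5. PROC FREQ counts responders from ALL. The counts pass through PROC TRANSPOSE and PROC STDRATE to PROC MIANALYZE.

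The code marks a "PLACE TO ADD DATA HANDLING AND MERGING STEPS", but that comes before step 2 and cannot redirect steps 4 and 5. ALL is named three times in the analysis block, so a slip in text extraction is unlikely.

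The flow was emulated on six made-up subjects, three per arm, with one non-COVID missing value in each arm and one COVID missing value in the active arm. Reading ALL, as printed, gives 2/3 placebo and 3/3 active responders. Reading ALLF gives 1/3 and 2/3, which is what the rule requires.

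**Illustrative size at Week 24**

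The plan gives no figure on this point to reproduce. The response rates below use the planning inputs in SAP Section 2.4 (mean change 0% on placebo, 40% reduction on active, SD 54.8%) and treat percent change as normal:

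- F-VASI 50: active Φ((−50+40)/54.8) = 0.4276; placebo Φ(−50/54.8) = 0.1808; difference 0.2468.
- F-VASI 75: active Φ((−75+40)/54.8) = 0.2615; placebo Φ(−75/54.8) = 0.0856; difference 0.1760 from unrounded rates.

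Let p be an arm's response rate, m the share missing for reasons other than COVID-19/MAR, and f the imputed response rate of those subjects relative to their arm's rate, with the same f in both arms. NRI-MI gives p(1−m) and plain MI gives p(1−m) + f·p·m, so

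plain MI − NRI-MI = f(pA·mA − pP·mP).

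Week 24 is the last Period 1 visit, so the before-and-after exception cannot apply there and only the override is lost. At earlier visits both are lost. The values of m and f are assumptions. With f = 1:

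| Missing, active / placebo | F-VASI 50: plain MI vs NRI-MI | F-VASI 75: plain MI vs NRI-MI |
|---|---|---|
| 5% / 5% | 0.247 vs 0.234 (+1.2 points) | 0.176 vs 0.167 (+0.9) |
| 10% / 10% | 0.247 vs 0.222 (+2.5) | 0.176 vs 0.158 (+1.8) |
| 20% / 20% | 0.247 vs 0.197 (+4.9) | 0.176 vs 0.141 (+3.5) |
| 20% / 5% | 0.247 vs 0.170 (+7.6) | 0.176 vs 0.128 (+4.8) |
| 5% / 20% | 0.247 vs 0.262 (−1.5) | 0.176 vs 0.180 (−0.4) |

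With equal missingness the inflation factor is (1−m(1−f))/(1−m). At f = 0 it is 1.00; at f = 0.5 it runs from 1.026 (m = 5%) to 1.125 (m = 20%); at f = 1 it runs from 1.053 to 1.250. The sign reverses when mP/mA exceeds pA/pP, which is 0.4276/0.1808 = 2.37 for F-VASI 50 and 0.2615/0.0856 = 3.06 for F-VASI 75 (ratios from unrounded rates).

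**Separate coding caution**

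The event count is taken directly from the transposed responder column, so an arm-by-stratum cell with no responders gets a missing value instead of 0. If 40 placebo subjects were spread evenly over the 8 strata, about 5 per cell, the chance of such a cell would be (1−0.1808)^5 = 0.37 for F-VASI 50 and (1−0.0856)^5 = 0.64 for F-VASI 75. The documents do not say how the procedure treats a missing count, so no bias is claimed.

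**The case against.** The strongest reply is that the SAP's rule is not in doubt. The prose states it several times, and the code itself contains the override. The block is labelled as a sample and cannot run as printed: merge steps are left out, it shows one endpoint, one visit and one dose comparison, and the faulted line overwrites ALL with two arms, so a programmer must rework it for the other doses. One analysis block apparently serves both MI and NRI-MI, and a shared block can name only one input. All of this lowers the likelihood of harm. It does not remove the contradiction, because the name printed belongs to the path that is not planned for responder endpoints.

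Several conditions must also hold together. With no COVID-19/MAR missing data, Section 9.1 uses the NRI dataset. The override applies only to what remains after the MAR exception, and the documents do not say how large that share is. This stands, and every figure above depends on it.

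The normal model is rough. Improvement cannot exceed 100%, yet the model puts Φ(−60/54.8), about 13.7%, of active subjects below −100%, which is over half of its 26.2% active F-VASI 75 rate. The sizes are therefore illustrative. The trace does not rest on them.

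**Conclusion.** The concern holds. As printed, the sample code contradicts the NRI-MI rule: the override reaches no estimate, and the responder analysis is plain MI. Certainty about the contradiction is high. Its effect is conditional: COVID-19/MAR missing data must exist, the 30 imputed datasets must differ, and there must also be values missing for other reasons.

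Under the planning rates and equal missingness of 5% to 20%, the plain-MI difference is 1.00 to 1.25 times the NRI-MI difference, but the direction is not fixed when missingness differs by arm. Values of f above 1, or different f by arm, are possible and are not covered. No size is given for T-VASI 50, for which the plan states no assumptions. The primary MMRM analysis is unaffected. Production programs are not visible, so this is a risk in the template that should be corrected, not evidence of a wrong result.

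**What to change.** In SAP Appendix E Section 3.0, make the treatment-subset step of the NRI-MI analysis read ALLF, let PROC FREQ count from that subset, and keep ALL for a clearly labelled plain-MI branch. Writing the subset to a new dataset name would also avoid overwriting the four-arm data. Separately, set the event count with `CASE=SUM(RESP1,0)` so that a cell without responders counts as 0. If production programs were built from this template, check which dataset their responder analyses read.

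The cost is two or three lines of sample code. The design, endpoints and governing prose do not change. Compared with the printed code, responder differences may become smaller or larger, depending on missingness by arm.
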